13.5.2 SAEs During Pregnancy

If the outcome of the pregnancy meets a criterion for immediate classification as an SAE - spontaneous abortion (any congenital anomaly detected in an aborted foetus is to be documented), stillbirth, neonatal death, or congenital anomaly—the Investigator should repeat the procedures for expedited reporting of SAEs as outlined in section 13.2.2 (Serious Adverse Events (SAEs)).

13.5.3 Pregnancy Report Processing at LEEDS CTRU

LEEDS CTRU will fax all Pregnancy Reports concerning exposure to Carfilzomib to Amgen within 1 business day.

LEEDS CTRU will submit a report to the MHRA and the REC should the pregnancy outcome meet the definition of a SUSAR. Refer to section 13.3 (SUSARs) for details.

13.6 Development Safety Update Reports (DSURs)

Safety data obtained from the trial will be included in DSURs that LEEDS CTRU will submit to the MHRA and the REC.

LEEDS CTRU will provide Amgen with DSURs that include information regarding Carfilzomib.

14.0 Withdrawal of patients

In consenting to the trial, patients are consenting to trial treatment, assessments, trial follow-up and data collection.

14.1 *Discontinuation of Trial Treatment*

14.1.1 Withdrawal due to clinical reasons

The site investigator may withdraw a patient from the trial treatment whenever continued participation is no longer in the patient's best interests, but the reasons for doing so must be recorded. Reasons for discontinuing treatment may include:

- Disease progression whilst on therapy
- Unacceptable toxicity
- Intercurrent illness which prevents further treatment
- The patient withdraws consent to further treatment
- Any alterations in the patient's condition which justifies the discontinuation of treatment in the site investigator's opinion

In these cases patients remain within the trial for the purposes of follow-up and data analysis according to the treatment option to which they have been allocated and for allowing existing collected data to be used. If the patient gives a reason for their withdrawal, this should be recorded.

14.1.2 Patient withdrawal from trial treatment

If a patient expresses their wish to withdraw from trial treatment, sites should explain the importance of remaining on trial follow-up, or failing this of allowing routine follow-up data to be used for trial purposes and for allowing existing collected data to be used. If the patient gives a reason for their withdrawal, this should be recorded.

14.2 *Future Data Collection*

If a patient explicitly states that they do not wish to contribute further data to the trial their decision must be respected, with the exception of safety data, and recorded on the relevant CRF. In this event details should be recorded in the patient's hospital records, no further CRFs must be completed and no further data other than safety data sent to LEEDS CTRU.

14.3 *Losses to follow-up*

If a patient moves from the area, every effort should be made for the patient to be followed up at another participating trial site and for this new site to take over the responsibility for the patient. Details of participating trial sites can be obtained from the LEEDS CTRU trial team who must be informed of the transfer of care and follow up arrangements.

15.0 Trial Closure

15.1 *End of Trial*

For regulatory purposes the end of the trial is defined as the date of the last participant's last data item. At this point, the end of trial notification will be submitted to the relevant regulatory authorities (e.g. UK MHRA) and ethics committees.

Following this, LEEDS CTRU will advise sites on the procedure for closing the trial at the site.

15.2 *Early discontinuation of trial*

The trial may be stopped before completion as an Urgent Safety Measure on the recommendation of the SRC. Sites will be informed in writing by LEEDS CTRU of reasons for early closure and the actions to be taken with regards the treatment and follow up of patients.

15.3 *Withdrawal from trial participation by sites*

Should a site choose to close to recruitment the PI must inform LEEDS CTRU in writing. Follow up as per protocol must continue for all patients recruited into the trial at that site.

15.4 *Archiving of Trial Documentation*

At the end of the trial, the LEEDS CTRU will archive securely all centrally held trial related documentation for a minimum of 15 years. Arrangements for confidential destruction will then be made. It is the responsibility of PIs to ensure data and all essential documents relating to the trial held at site are retained for a minimum of 15 years after the end of the trial, in accordance with national legislation and for the maximum period of time permitted by the site.

Essential documents are those which enable both the conduct of the trial and the quality of the data produced to be evaluated and show whether the site complied with the principles of Good Clinical Practice and all applicable regulatory requirements.

LEEDS CTRU will notify sites when trial documentation held at sites may be archived. All archived documents must continue to be available for inspection by appropriate authorities upon request.

16.0 Trial Monitoring and Oversight

Participating sites and PIs must agree to allow trial-related on-site monitoring, Sponsor audits and regulatory inspections by providing direct access to source data/documents as required. Patients are informed of this in the patient information sheet and are asked to consent to their medical notes being reviewed by appropriate individuals on the consent form.

LEEDS CTRU will determine the appropriate level and nature of monitoring required for the trial. Risk will be assessed on an ongoing basis and adjustments made accordingly.

16.1 Central monitoring

UK NAC will be requested to submit screening logs for the trial to LEEDS CTRU on request. UK NAC and RHC/sites will be requested to submit staff delegation logs for the trial to LEEDS CTRU at the frequency detailed in the trial monitoring plan or on request and these logs will be checked for consistency and completeness. Also refer to sections 4.2.2 (Required documentation).

Ensuring patient eligibility is the responsibility of the UK NAC PI and confirmation by the Site (RHC) PI or other delegated Investigator(s). Checks of the criteria listed on the registration form will be undertaken by an appropriately trained LEEDS CTRU staff member prior to registration. Also refer to section 7.1 (Registration).

UK NAC will be required to maintain a log of all patient informed consent forms that have been completed at site (regardless of whether the patient is subsequently registered to the trial). This log will include details of the versions of informed consent form/patient information sheet used, patient completion of the consent form, the name of the person taking consent, etc. A copy of the log must be submitted to LEEDS CTRU at the frequency detailed in the trial monitoring plan or on request. Also refer to section 5 (Informed Consent).

Copies of completed drug accountability logs will be collected at LEEDS CTRU for all trial patients. Sites will be required to submit logs on request. A proportion of these will be monitored centrally, as per the monitoring plan, to ensure completeness and correlation with data captured in the CRF. Also refer to section 9.3 (pharmacy responsibilities).

Participating RHC/sites (and UK NAC in its role as a RHC/site) will be requested to conduct quality control checks of documentation held within the Investigator Site File and Pharmacy Site File at the frequency detailed in the trial monitoring plan. Checklists detailing the current version/date of version controlled documents will be provided for this purpose.

Data received at LEEDS CTRU will be subject to review in accordance with section 12 (Data Management and Data Handling Guidelines).

Where central monitoring of data and/or documentation submitted by sites indicates that a patient may have been placed at risk (e.g. evidence of an overdose having been administered, indication that stopping rules for an IMP were not observed following an adverse reaction, etc.), the matter will be raised urgently with site staff and escalated as appropriate (refer to section 17 (Incident Reporting and Serious Breaches) and 16.2 ('For cause' on-site monitoring) for further details).

16.2 'For Cause' On-Site Monitoring

On-site monitoring visits may be scheduled where there is evidence or suspicion of non-compliance at a site with important aspect(s) of the trial protocol/GCP requirements. Sites will be sent a letter in advance outlining the reason(s) for the visit. The letter will include a list of the documents that are to be reviewed, interviews that will be conducted, planned inspections of the facilities, who will be performing the visit and when the visit is likely to occur.

Following a monitoring visit, the Trial Monitor/Trial Coordinator will provide a report to the site, which will summarise the documents reviewed and a statement of findings, deviations, deficiencies, conclusions, actions taken and actions required. The PI at each site will be responsible for ensuring that monitoring findings are addressed in a timely manner, and by the deadline specified.

LEEDS CTRU will assess whether it is appropriate for the site to continue participation in the trial and whether the incident(s) constitute a serious breach. Refer to section 17 (Incident Reporting and Serious Breaches) for details.

16.3 Oversight Committees

16.3.1 Trial Management Group (TMG)

The TMG will include the Chief Investigator, clinicians and experts from relevant specialities and CATALYST trial staff from LEEDS CTRU (see Page 3). The TMG will be responsible for overseeing the trial. The group will meet regularly and will send updates to PIs (via newsletters and/or at Investigator meetings) and to the NCRI Myeloma Clinical Studies Group.

The TMG will review substantial amendments to the protocol prior to submission to the REC and MHRA. All PIs will be kept informed of substantial amendments through their nominated responsible individuals.

Members of the TMG will be asked to sign a TMG charter outlining their duties and responsibilities.

The TMG, comprising the Chief Investigator, CTRU team and co-investigators (see page 3) will be assigned responsibility for the clinical set-up, on-going management, promotion of the trial, and for the interpretation of results. Specifically the TMG will be responsible for (i) protocol completion, (ii) CRF development, (iii) obtaining approval from the main REC and supporting applications for Site Specific Assessments, (iv) submitting a CTA LRECs, (v) submitting a DDXt to trial participations by responsible individuals from the research staff or from regulatory application and obtaining approval from the MHRA, (vi) completing cost estimates and project initiation, (vii) facilitating the Dose Escalation Review Group, (viii) reporting of serious adverse events, (ix) monitoring of screening, recruitment, treatment and follow-up procedures, (x) auditing consent procedures, data collection, trial end-point validation and database development. During the dose escalation phase, the TMG along with at least one investigator from each recruiting site (PI or delegate), a company representative (when available) and non-recruiting clinician(s) (where available) will review the safety and ethics of the study by regularly reviewing safety data during the dose escalation phase. The decision about whether to expand the cohort or open up the next level will be based on the frequency of observed toxicity and the definitions of DLT and MTD in section 8. The group will meet or communicate via teleconference approximately monthly.

16.3.2 Safety Review Committee

The Safety Review Committee, comprising the Chief Investigator, at least one investigator from each recruiting site (PI or delegate), CTRU statistician(s), Senior Trial Co-ordinator, a company representative (when available) non-recruiting clinician(s) will regularly review the safety and ethics of the study during the dose escalation phase to provide independent advice on data and safety aspects of the trial. The decision about whether to expand the cohort or open up the next level will be based on the frequency of observed toxicity and the definitions of DLT and MTD in Section 8. The Group will meet or communicate via teleconference approximately monthly. Additionally, the Group will periodically review safety reports throughout the dose expansion phase of the trial. Members of the IDMC will be asked to sign a SRC charter outlining their duties and responsibilities.

16.3.3 Role of LEEDS CTRU

The CTRU will provide set-up and monitoring of trial conduct to CTRU SOPs, and the GCP Conditions and Principles as detailed in the UK Medicines for Human Use (Clinical Trials) Regulations including, registration design and service, database development and provision, protocol development, CRF design, trial design, source data verification, monitoring schedule and statistical analysis for the trial. In addition the CTRU will support IRAS and NIHR CSP submissions and clinical set-up, ongoing management including training, monitoring reports and promotion of the trial. The CTRU will be responsible for the day to day running of the trial including trial administration, database administrative functions, data management, safety reporting and all statistical analyses.

17.0 Incident Reporting and Serious Breaches

17.1 Incident Reporting

The trial will be conducted in accordance with the principles of Good Clinical Practice in clinical trials, as applicable under UK regulations, the NHS Research Governance Framework (and Scottish Executive Health Department Research Governance Framework for Health and Social Care 2006 for studies conducted in Scotland), and through adherence to CTRU Standard Operating Procedures (SOPs).

Organisations must notify LEEDS CTRU of all deviations from the protocol or GCP immediately. LEEDS CTRU may require a report on the incident(s) and a form will be provided if the organisation does not have an appropriate document (e.g. Trust Incident Form for UK sites).

If site staff are unsure whether a certain occurrence constitutes a deviation from the protocol or GCP, the LEEDS CTRU trial team can be contacted immediately to discuss.

LEEDS CTRU will assess all incidents to see if they meet the definition of a serious breach.

Each site must also report according to their trust incidence reporting policies.

17.2 Serious Breaches

CTRU and Sponsor have systems in place to ensure that serious breaches of GCP or the trial protocol are picked up and reported. Investigators are required to promptly notify the CTRU of a serious breach (as defined by Regulation 29A of the Medicines for Human Use (Clinical Trials) Regulations 2004 [Statutory Instrument 2004/1031], as amended by Statutory Instrument 2006/1928) that they become aware of. A “serious breach” is a breach which is likely to effect to a significant degree –

- the safety or physical or mental integrity of the participants of the trial; or
- the scientific value of the trial.

For further information, the Investigator should contact the CTRU.

Systematic or persistent non-compliance by a site with GCP and/or the protocol, including failure to report SAEs occurring on trial within the specified timeframe, may be deemed a serious breach.

In cases where an actual serious breach has been identified, LEEDS CTRU will inform the MHRA within 7 calendar days of becoming aware of the breach.

Sites must notify the CTRU of serious breaches (MHRA Guidance on the Notification of Serious Breaches). The CTRU will notify the sponsor of all serious breaches.

Leeds CTRU will use an organisation’s history of non-compliance to make decisions on future collaborations.

18.0 Endpoints

18.1 Primary endpoints

Dose-Limiting Toxicities (Dose escalation phase), between the time of receiving the first registered dose of Carfilzomib in cycle 1 and day 1 cycle 2, in order to establish the Maximum Tolerated Dose (MTD) and recommended dose (RD) of Carfilzomib in combination with Thalidomide and Dexamethasone.

Proportion of patients treated who experience any grade 3 or 4 CTCAE toxicity throughout all treatment cycles

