8.1.4 Dose Limiting Toxicities

Dose limiting toxicities (DLTs) will be collected from the time of receiving the first dose of Carfilzomib in cycle 1 up to the first dose of treatment administered in cycle 2. Only DLTs that are attributed to the registered dose of Carfilzomib will be included when determining the MTD (i.e those attributed to the loading dose will be excluded) (see section 19.2). A DLT will be defined as any of the following events that are determined to be related to trial drug administration:

1. Any non-haematological toxicity ≥ Grade 3 according to NCI CTCAE Version 4.03 which fails to return to ≤Grade 1 or baseline after 7 days. Nausea, vomiting, diarrhoea and electrolyte imbalances will be considered DLTs only if they reach ≥ Grade 3 severity despite adequate supportive care measures. Similarly, fluid retention or worsening symptoms of heart failure will be considered as DLTs if they are persistent ≥Grade 3 despite increase in oral diuretics or there is an increase in dyspnoea by ≥ 2 NYHA grades within 12 hours of administration of Carfilzomib which persists for > 6 hours or needs hospital admission
2. Grade 4 neutropenia lasting > 7 days or Grade 4 neutropenia with sepsis despite adequate supportive measures.
3. Any grade 4 thrombocytopenia which fails to return to Grade 2 within 7 days without platelet support
4. Delay of >8 days within cycle 1 or delay of commencement of 2nd cycle by more than 14 days, due to significant toxicity or tolerability issue*
5. Any other event which, in the opinion of the Safety Review Committee, is considered to be clinically significant and related to treatment

*This will not be defined as a DLT if the delay is due to one of the other specified DLT criteria.

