13.2 Reporting Procedures

13.2.1 All Adverse Events (AEs)

All adverse events that occur between informed consent and 30 days post last trial treatment administration must be recorded in the patient notes and the trial CRFs. Those meeting the definition of a Serious Adverse Event (SAE) must also be reported to LEEDS CTRU within 24 hours of becoming aware of the event using the trial specific SAE Report. Also refer to section 13.2.2 (Serious Adverse Events (SAEs)).

Pre-existing conditions do not qualify as adverse events unless they worsen.

Overdoses

All accidental or intentional overdoses, whether or not they result in adverse events, must be recorded in the patient notes and CRFs. Overdoses resulting in an adverse event are classified as SAEs and must be reported to LEEDS CTRU according to SAE reporting procedures. The fact that an overdose has occurred must be clearly stated on the SAE Report. Also refer to section 13.2.2 (Serious Adverse Events (SAEs)).

Sites must inform LEEDS CTRU immediately when an overdose has been identified. Also refer to section 17 (Incident Reporting and Serious Breaches).

Adverse Event Term

An adverse event term needs to be provided for each adverse event, preferably using the term listed in the Common Terminology Criteria for Adverse Events (CTCAE) version 4.03, available online at: http://evs.nci.nih.gov/ftp1/CTCAE/CTCAE_4.03_2010-06-14_QuickReference_8.5x11.pdf

Severity

Severity for each adverse event will be determined by using the Common Terminology Criteria for Adverse Events (CTCAE) version 4.03 as a guideline, wherever possible. The criteria are available online at: http://evs.nci.nih.gov/ftp1/CTCAE/CTCAE_4.03_2010-06-14_QuickReference_8.5x11.pdf. Appendix 5 also details some toxicity criteria.

In those cases where the CTCAE criteria do not apply, severity should be coded according to the following criteria:

- 1 = Mild (awareness of sign or symptom, but easily tolerated)
- 2 = Moderate (discomfort enough to cause interference with normal daily activities)
- 3 = Severe (inability to perform normal daily activities)
- 4 = Life threatening (immediate risk of death from the reaction as it occurred)
- 5 = Fatal (the event resulted in death)

Causality

The PI, or other delegated site investigator, must perform an evaluation of causality for each adverse event. Causal relationship to each trial treatment must be determined as follows:

- **None**
There is no evidence of any causal relationship.
- **Unlikely**

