18.3 Endpoint definitions

- DLT and MTD are defined in section 8.1.4 and 8.1.5
- The proportion of patients treated who experience any grade 3 or 4 CTCAE toxicity will be calculated as number of patients who experience any grade 3 or 4 CTCAE toxicity throughout their treatment cycle.
- Clonal response rate (based on paraprotein and FLCs) is defined as the proportion of patients who achieve at least a PR within 3 months, at 3 months, within 6 months and at 6 months after trial registration.
- Amyloidotic organ response rate is defined as the proportion of patients who achieve organ response within 3 months and within 6 months of trial registration.
- Time to Amyloidotic organ response is defined as the time from the dose allocation to first achieving organ response.
- The number of patients experiencing dose delays will be defined as the number of patients experiencing delays in treatment with any of the study treatments.
- KTD compliance: Patients will be regarded as compliant to treatment where treatment is received as per protocol until withdrawal from treatment and have no more than 1 dose omission of Carfilzomib, 5 of Thalidomide or 1 of Dexamethasone during each cycle.
- Relative Dose intensity will be calculated as the percentage ratio between the received and planned dose intensities, where dose intensity is the cumulative dose divided by the duration of treatment.

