2.3 Derivation of endpoints

2.3.1 Primary endpoints

Dose limiting toxicities (DLTs) will be collected from the time of receiving the first dose of Carfilzomib in cycle 1 up to the first dose of treatment administered in cycle 2. Only DLTs that are attributed to the registered dose of Carfilzomib will be included when determining the MTD. A DLT will be defined as any of the following events that are determined to be related to trial drug administration:

1. Any non-haematological toxicity \geq Grade 3 according to NCI CTCAE Version 4.03 which fails to return to \leq Grade 1 or baseline after 7 days. Nausea, vomiting, diarrhoea and electrolyte imbalances will be considered DLTs only if they reach \geq Grade 3 severity despite adequate supportive care measures. Similarly, fluid retention or worsening symptoms of heart failure will be considered as DLTs if they are persistent \geq Grade 3 despite increase in oral diuretics or there is an increase in dyspnoea by \geq 2 NYHA grades within 12 hours of administration of Carfilzomib which persists for $>$ 6 hours or needs hospital admission
2. Grade 4 neutropenia lasting $>$ 7 days or Grade 4 neutropenia with sepsis despite adequate supportive measures.
3. Any grade 4 thrombocytopenia which fails to return to Grade 2 within 7 days without platelet support
4. Delay of $>$ 8 days within cycle 1 or delay of commencement of 2nd cycle by more than 14 days, due to significant toxicity or tolerability issue*
5. Any other event which, in the opinion of the Safety Review Committee, is considered to be clinically significant and related to treatment

The MTD is defined as the highest dose level at which no more than 1 patient experiences a DLT, from the time of receiving the first registered dose of Carfilzomib in cycle 1 up to the first dose of treatment administered in cycle 2, i.e. the dose level below that at which 2 or more patients experiences a DLT. If no more than one patient experiences a DLT at the highest dose level then this will be considered as the MTD.

Once the MTD has been established, a minimum of 6 patients will be treated at this dose level in order to establish the RD. The RD is the dose which will be used in the dose expansion phase of the study to evaluate activity.

The proportion of patients treated who experience any grade 3 or 4 CTCAE toxicity will be calculated as number of patients who experience any grade 3 or 4 CTCAE toxicity throughout their treatment cycle.

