5.1 General calculations

Unless otherwise stated, percentages will be calculated using the total number of patients in the appropriate population as the denominator (i.e. including all patients with missing data for that variable). All analyses will be carried out using SAS unless stated otherwise.

All percentages and means will be rounded to 1 decimal place and standard deviations to 2 decimal places. Values that are below the limit of detection and therefore non-quantifiable will be summarised using the limit of quantification value. For listings, if required, the non-quantifiable value would be reported as an inequality.

Summaries are divided into those participants treated at the recommended dose either during the dose escalation phase (prior to the identification of the recommended dose) or during the dose expansion phase (RD population), and all other participants treated during the dose escalation phase at dose levels other than the recommended dose (Non-RD population). The non-RD population will be split by dose level.

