5.3.2 Primary endpoints

The number of patients experiencing DLTs within the first cycle of KTD will be presented, with descriptive summaries of the specific DLTs observed. Summaries will be presented for each dose level. This data will be presented for patients registered to the dose escalation phase of the study only.

Further summaries of longer-term tolerability will also be presented for patients registered to the dose escalation phase to include the maximum toxicity grade experienced within the first three cycles of treatment, overall and by cycle. Individual listings of the toxicities, grade and cycle of all toxicities experienced within the first three cycles will be presented.

The number of patients experiencing any grade 3 or 4 CTCAE toxicity within all cycles of treatment will be summarised. This will be presented overall and by dose cohort, across all cycles as well as by each cycle.

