5.3.2 Secondary endpoints

Safety and toxicity profiles for each cycle and cohort: data will be summarised descriptively, including the proportion of patients experiencing at least one SAE, the number of SAEs experienced per participant, and the number of SAEs experienced according to seriousness criteria, causality, and body system. Toxicity will be summarised according to CTCAE grades and will be summarised as the maximum grade toxicity experienced within each cycle, and overall.

The proportion of patients achieving at least a PR (clonal response) within 3m, at 3m, within 6m and at 6m and the proportion of patients achieving an amyloidotic organ response within 3m and 6m will be presented in tabulated form. Corresponding 90% and 95% confidence intervals will also be presented. Responses at 3 and 6 months will be broken down by response achieved, and by organ (for organ response).

Time to amyloidotic organ response and time to maximum response will be calculated using the Kaplan Meier method. Median time to amyloidotic organ response and median time to maximum response will be presented, with corresponding 95% confidence intervals.

The proportion and number of patients alive at 6 months and patients progression free at 6 months will be presented with corresponding 90% and 95% confidence intervals. If appropriate, Kaplan Meier curves for progression free survival may be explored.

Each patient will be assessed for their maximum clonal response; the number and proportion of participants in each response category within 6 cycles of treatment will be presented with corresponding 95% confidence intervals. Patients who do not achieve a maximum response will be summarised as, "no maximum response".

Feasibility of delivering treatment according to protocol schedule will be summarised descriptively to include the number of patients requiring dose delays and/or reductions, the number of patients withdrawing from treatment, and reasons for dose delays / reductions and withdrawals. Time on treatment and reasons for stopping treatment will also be presented. The number of doses missed will be summarised overall and by cycle.

6. Reporting and Dissemination of the Results

Final analysis will be carried out after the last participant's last data item.

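### The primary safety proportion counts only grade 3 or 4 toxicity, so a patient whose only severe event is fatal (grade 5) is scored as having none

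*Protocol*

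**What the plan says.** Protocol section 18.1 gives the second primary endpoint as "Proportion of patients treated who experience any grade 3 or 4 CTCAE toxicity throughout all treatment cycles". Section 18.3 says that it "will be calculated as number of patients who experience any grade 3 or 4 CTCAE toxicity throughout their treatment cycle". The SAP does not widen this. Its section 2.1 repeats the definition, section 2.3.1 begins "The proportion of patients treated who experience any grade 3 or 4 CTCAE toxicity will be calculated as number of patients", and the analysis text in section 5.3.2 (primary endpoints) reads "The number of patients experiencing any grade 3 or 4 CTCAE toxicity within all cycles of treatment will be summarised". Protocol sections 1.1 and 19.3 name the same two grades. None of these places says how a grade 5 event is counted.

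Three other passages bear on the reading:

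- **Severity scale.** Protocol section 13.2.1 separates life-threatening (4) from fatal: "5 = Fatal (the event resulted in death").
- **Denominator.** SAP section 5.1 states that "percentages will be calculated using the total number of patients in the appropriate population as the denominator".
- **The other primary endpoint.** The first DLT criterion in Protocol section 8.1.4 starts from "Any non-haematological toxicity ≥ Grade 3 according to NCI CTCAE Version 4.03", with no upper limit on grade.

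**The concern.** A proportion meant to describe severe toxicity should not score the most severe outcome as no event. A sudden toxic death with no separately recorded grade 3 or 4 event adds nothing to the numerator and one to the denominator. It also removes any chance of that patient contributing a later grade 3 or 4 event.

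This matters most in the expansion phase. Its stated purpose (Protocol sections 3.1 and 19.1) is to assess safety further at the RD. The DLT summary is restricted to escalation patients (Protocol section 19.3, SAP section 5.3.2), so for the 20 expansion patients this proportion is the only primary safety measure. The scenario is plausible: Protocol section 10.12 describes fatal thromboembolic, TTP/HUS and tumour lysis events with carfilzomib.

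**Working it through.** **No planned figure to reproduce.** The documents give no target rate, precision or threshold for this endpoint. What can be computed is the effect of the definition.

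**Inputs**

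- Expansion patients at the RD: 20 (Protocol section 19.1).
- Escalation patients at the RD: at least 6 (Protocol section 8.1.3, Table 2). Planned RD cohort: 6 + 20 = 26.
- Maximum escalation size: 3 levels × 6 = 18, matching Protocol section 19.1. Maximum total: 18 + 20 = 38.
- x = patients with any grade 3 or 4 event; k = patients whose only event of grade 3 or above is grade 5.

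**Formula**

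As defined, the proportion is x/n. Counting grades 3 to 5, it is (x + k)/n. The understatement is k/n, whatever the value of x.

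| Denominator n | Understatement per fatal-only patient, 1/n |
|---|---|
| 20 (expansion only) | 5.0 points |
| 26 (planned RD cohort) | 3.8 points |
| 38 (maximum total) | 2.6 points |

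**Illustration, assuming x = 10 in n = 26** (exact Clopper-Pearson 95% intervals, added here for scale)

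| k | Counting grades 3 to 5 | 95% interval |
|---|---|---|
| 0 (same as the current definition) | 10/26 = 38.5% | 20.2 to 59.4 |
| 1 | 11/26 = 42.3% | 23.4 to 63.1 |
| 2 | 12/26 = 46.2% | 26.6 to 66.6 |

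**How many such patients?** The documents give no fatal-only rate r for KTD, so r is an assumption. The expected number is 26r, and the chance of at least one is 1 − (1 − r)^26.

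| Assumed r | Expected patients | Chance of at least one |
|---|---|---|
| 2% | 0.5 | 41% |
| 4% | 1.0 | 65% |
| 20% | 5.2 | over 99% |

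The 4% is borrowed from the treatment-related mortality of the melphalan-dexamethasone trial in Protocol section 2.1.2. The 20% is deaths on study from any cause with a lenalidomide-cyclophosphamide-dexamethasone regimen in the same section; it marks the end of the range and is not a realistic fatal-only rate.

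**The case against.** The strongest reply is that fatal toxicity remains visible. Toxicity is also "summarised as the maximum grade toxicity experienced within each cycle, and overall" (SAP section 5.3.2, secondary endpoints). SAEs are tabulated by seriousness criterion and causality, and resulting in death is one of those criteria (Protocol section 13.1). Escalation patients have listings of every toxicity with its grade for cycles 1 to 3. Deaths at 6 months are a secondary endpoint. All of this stands. A reader might infer that toxic deaths surface only in the 6-month count; the documents do not support that. Even so, none of these tables changes the primary proportion. The 6-month count is not limited to toxicity. If it is handled as an efficacy endpoint, it uses the per protocol set, which requires a post-baseline efficacy assessment, so an early toxic death could drop out there too.

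Second, the analysis is descriptive and no decision rule uses this proportion: escalation and the choice of RD rest on DLTs, and the safety committees review data throughout. This also stands. It limits the consequence to the reported estimate, so a reader should not infer that the wording could steer dose selection.

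Third, several cited carfilzomib studies, including the KTd study in Protocol section 2.1.3.3, report grade 3/4 events, so the wording follows a common habit. But the same section cites a carfilzomib combination study reporting grades 3 to 5, and others in sections 2.1.3.3 and 2.1.3.4 report grade 3 or higher. The quoted five-point scale is the fallback where CTCAE criteria do not apply, yet it shows that the protocol treats fatal as a grade of its own.

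Finally, DLT criteria serve a different purpose and use grade 4 thresholds for neutropenia and thrombocytopenia. Full alignment was never intended; the contrast concerns only whether the grade range is closed at the top.

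**Conclusion.** The point holds on the wording, which is the same in both documents and is not corrected elsewhere. The primary safety proportion omits a patient whose only event of grade 3 or above is fatal. A fatal case with a separate grade 3 or 4 record is still counted.

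The size is 3.8 points per such patient in an RD cohort of 26 and 5.0 points in the 20 expansion patients. At an assumed 4% fatal-only rate, about one such patient is expected. That shift is small beside the sampling uncertainty shown above, but its direction is known and it favours the regimen. The figure of 26 assumes exactly 6 escalation patients at the RD, with all 26 in the safety analysis set and each receiving at least one dose at the RD.

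A reader might take the 20% on-study death rate and infer an understatement of up to 5/26 = 19 points. The documents do not support that. The 20% is all-cause mortality on another regimen. The calculation also needs every death to be a toxicity in a patient with no grade 3 or 4 event, although the same study reports non-haematological toxicity of grade 3 or above in 71%. The carfilzomib study in AL amyloidosis (Protocol section 2.1.3.4) reported no deaths.

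**What to change.** Replace 'any grade 3 or 4' with 'any grade 3 or higher (grades 3 to 5)' in Protocol sections 1.1, 18.1, 18.3 and 19.3, and in SAP sections 2.1, 2.3.1 and 5.3.2 (primary endpoints). Show grade 5 as its own row in the overall and by-cycle tables. The grade 3 or 4 count can stay as a supporting row for comparison with studies that report it that way.

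The cost is wording only. Adverse events are already graded and collected to 30 days after the last treatment (Protocol section 13.2.1), and no sample size is derived from this endpoint. The downside is a possibly slightly less favourable reported rate. Making the change before analysis avoids deciding how to count deaths once they are known, in an open-label trial.
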